### 3. STUDY PLAN AND PROCEDURES

#### 3.1 Overall study design and flow chart

This study is designed as a 5-year, randomized, open, parallel-group multicentre trial with a 5-year prolongation with the objectives to estimate the efficacy and tolerability of esomeprazole compared with anti-reflux surgery, in a long-term treatment of adult subjects with confirmed, symptomatic gastroesophageal reflux disease with or without esophagitis (objectively documented by endoscopy and abnormal 24 hour pH metry). All subjects should be eligible for surgery.

The study will begin with a 12-week run-in period enabling the recording of baseline values and responses to medical treatment with esomeprazole 40 mg o.d. This period will end with a randomization into the 10-year study period. All subjects should have the need for continuous treatment to control reflux and be eligible for anti-reflux surgery. Subjects should not have more than LA grade B endoscopic-visualized mucosal breaks or more than mild symptoms of GERD prior randomization and should have responded to esomeprazole treatment in the 12-week run-in period.

The 10-year study period consists of 2 treatment arms, medical treatment (esomeprazole, start dose is 20 mg o.d.) and anti-reflux surgery (laparoscopic fundoplication). Subjects willing to accept randomization to either surgery or long-term medical treatment will receive treatment according to a randomization list.

*Helicobacter pylori* (*Hp*) status will be assessed based on biopsy material.

In case of confirmed peptic ulcer disease and positive *Hp* testing eradication therapy should be given prior to enrolment. Subject should not be enrolled within 3 months after therapy.

In case of a first episode of peptic ulcer disease during the 10-year study period and confirmed positive *Hp* testing eradication therapy is allowed.

In all other cases of *Hp* infection not associated with peptic ulcer disease eradication therapy is not allowed.

The planned number of subjects is 550 randomized in 11 countries, with at least 6 subjects per centre.

Visits 1, 2, 3, 4, 5, 6, 7, 8, 12, 16, 31, 33, 35, 37 and 39 will be regular visits with the investigator and visits 9, 10, 11, 13, 14 and 15 may be done by the study nurse.

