### **3.4.5 Pre-study, concomitant and post-study treatment(s)**

Subjects entering this study have most likely been on long-term treatment with various anti-acid secretion therapy (i.e. PPI, H2RA). During the 12 week run-in period the subject must undergo the “Investigational week” including endoscopy with biopsy sampling, 24 hr pH-metry, manometry, SAP and laboratory measurements. In order to get relevant pH measurements the study medication (esomeprazole 40 mg o.d.) must be stopped at least 7 consecutive days before the 24 hr pH-metry at visit 3. Subjects randomized to anti-reflux surgery should be treated with

esomeprazole (20 mg o.d. to 40 mg daily) before surgery (within three months from randomization).

Motility activators (prokinetic drugs) e.g. metoclopramide are allowed for operated subjects between visit 5 and visit 6 for treatment of post-operative intestinal paralysis.

In case of an ulceration/erosion in the fundoplication within 3 months post surgery, subjects are allowed to be treated with esomeprazole 40 mg o.d. for 2-12 weeks. Subjects in the surgical arm are instructed to take antacid/alginate medication if they experience dyspeptic symptoms after surgery. If the subject has need for additional medication he/she shall contact the investigator who may dispense 1 bottle of esomeprazole 20 mg to be taken on demand, not more than one tablet daily. Unused medication is to be returned on the following visit (visit 7) and drug accountability is to be recorded in the CRF. After visit 7 no such medication is allowed. Subjects in the surgical arm, who develop a gastric or duodenal ulcer due to intermittent usage of NSAID are allowed to be treated with esomeprazole 40 mg o.d. for 2 weeks.

Concerning *Hp* eradication please see Section 3.1.

Antacids and alginates are allowed during the study.

Other medication which is considered necessary for the subject's safety and well being may be given at the discretion of the investigator(s). The administration of all medication (including investigational products, antacids and alginates) must be recorded in the appropriate sections of the case report form (CRF).

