**Table 4 Safety objectives and endpoints relating to each objective**

Objective	Endpoints	Summary statistic for analysis (including timepoint and population)	Planned analysis	Significance of results
4.4.3 Laboratory screen variables	Laboratory assessments	
 
- Descriptive presentation of laboratory results for each sample occasion.
 
- Number of subjects with values below, within and above the reference range, over time.
 
- Median changes between baseline and the last visit for each laboratory variable.
 
- Graphs showing last visit values versus the baseline values for each laboratory variable.
 
-All clinical laboratory presentations will be made for the safety population.
 
	No formal statistical comparison.	The result will contribute to the determination of the adverse drug reaction pattern and frequency during long-term treatment with esomeprazole.
4.4.2 SAE and AE	Occurrence and nature (seriousness intensity and action taken to study drug due to AE) of all SAEs and AEs causing premature discontinuation of study drug and /or study.	
 
-Frequency of subjects with SAEs and AEs leading to discontinuation of study drug and/or study.
 
-AE pattern (e.g. by system organ classification)
 
- SAEs and discontinuations due to AE will be presented for the safety population
 
	No formal statistical comparison.	The result will contribute to the determination of the adverse drug reaction pattern and frequency during long-term treatment with esomeprazole.

The methods for collecting safety data are described below

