## **Serious Adverse Event**

A serious adverse event is an AE occurring during any study phase (i.e., run-in, treatment, washout, follow-up), and at any dose of the investigational product, comparator or placebo, that fulfils one or more of the following criteria:

- results in death
- is immediately life-threatening
- requires in-subject hospitalization or prolongation of existing hospitalization
- results in persistent or significant disability or incapacity
- is a congenital abnormality or birth defect
- is an important medical event that may jeopardize the subject or may require medical intervention to prevent one of the outcomes listed above

The causality of SAEs (i.e., their relationship to study treatment) will be assessed by the investigator(s), who in completing the relevant case report form must answer “yes” or “no” to the question “Do you consider that there is a reasonable possibility that the event may have been caused by the drug?” For further guidance on the definition of a SAE and a guide to the interpretation of the causality question, see Appendix F.

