#### 4.4.2.2 Recording of adverse events

SAEs and AEs causing premature discontinuation of study drug and/or study will be recorded retrospectively by the investigator in the Case Report Form at visit 2 and the following visits. If any SAE or AE causing premature discontinuation of study drug and/or study are ongoing at the subjects last visit in the study, they must be followed up after 2 to 4 weeks and thereafter as long as medically indicated. This can be done either as an extra visit to the clinic or by written or verbal contact with the subject.

Spontaneously reported SAEs and AEs causing premature discontinuation of study drug and/or study, objective findings and observations, and SAE and AEs causing premature discontinuation of study drug and/or study reported in response to the standardized question “Have you had any health problems since the previous visit?” will be recorded in the CRF. Start and stop date (or marked as ongoing), outcome, maximum intensity, seriousness, and action taken with regard to investigational product and if the AE caused subject to discontinue the study will be recorded. Maximum intensity will be rated according to the following scale:

- |              |  |
|--------------|--|
| 1 = Mild     | - awareness of sign or symptom, but easily tolerated                 |
| 2 = Moderate | - discomfort sufficient to cause interference with normal activities |
| 3 = Severe   | - incapacitating, with inability to perform normal activities        |

It is important to distinguish between serious and severe AEs. Severity is a measure of intensity whereas seriousness is defined by the criteria in Section 4.4.2.1. An AE of severe intensity need not necessarily be considered serious. For example, nausea, which persists for several hours, may be considered severe nausea, but not a SAE. On the other hand, a stroke which results in only a limited degree of disability may be considered a mild stroke but would be a SAE.

Abnormal test results from laboratory investigations or endoscopy investigations (including biopsies) that meet any criteria of an SAE must be reported in accordance with the SAE reporting procedures (see Section 4.4.2.3).

Symptoms included in the efficacy variables

- Section 4.3.5.1 GERD symptoms (i.e. heartburn, acid regurgitation, dysphagia)
- Section 4.3.5.1. other GI symptoms (i.e. epigastric pain, flatulence, bloating, ability to vomit, ability to belch, diarrhoea)

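### The count of AEs that stop drug or study is not like for like between arms: after visit 7 operated subjects normally have no study drug to stop, and for non-serious AEs the count is all-cause

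*Protocol*

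**What the plan says.** Section 3.1 describes the trial as one "with the objectives to estimate the efficacy and tolerability of esomeprazole compared with anti-reflux surgery", so tolerability is meant to be set against surgery. Section 4.4 limits safety data on events to SAEs and to AEs that cause premature discontinuation, and explains that visits are too far apart for good data on other non-serious events.

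For this endpoint Table 4 gives the summary statistic "Frequency of subjects with SAEs and AEs leading to discontinuation of study drug and/or study", in the safety population. The planned analysis is "No formal statistical comparison". The stated use is: "The result will contribute to the determination of the adverse drug reaction pattern and frequency during long-term treatment with esomeprazole". The safety analysis text in section 6.2.3 repeats the combined criterion, says only that the presentation is descriptive, and does not name treatment groups.

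On recording, section 4.4.2.2 lists dates, outcome, intensity and seriousness, and adds that "action taken with regard to investigational product and if the AE caused subject to discontinue the study will be recorded". Section 4.4.2.1 requires the investigator to give a yes/no causality answer for every SAE, and the question concerns the drug.

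On access to the drug, section 3.4.5 lets operated subjects have esomeprazole on demand for a time and then says: "After visit 7 no such medication is allowed". In Tables 1 and 2 the footnotes restrict dispensing from visit 7 onwards to the medical arm.

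**The concern.** A non-serious AE exists in the data only if something is stopped because of it. In the medical arm that can be the tablets or study participation. In an operated subject after visit 7 it is normally study participation alone. A non-serious event that leads a medical-arm subject to stop tablets is recorded. The same event in an operated subject who stays in the study is not. If the two frequencies are printed side by side, part of any gap comes from the recording rule and not from harm.

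At stake is what may be said about the tolerability of esomeprazole relative to surgery, and whether the non-serious part of the count can support the adverse-drug-reaction use that Table 4 gives it. The primary endpoint is not affected.

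**Working it through.** The protocol gives no figure to reproduce here, so the check sets its rules side by side, with one piece of arithmetic on time.

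**1. Routes into the non-serious AE count**

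| Period | Medical arm | Surgical arm |
|---|---|---|
| Randomization to surgery (within 3 months; sections 3.1, 3.4.2) | stop drug, or leave study | stop drug (esomeprazole allowed while waiting), or leave study |
| Surgery to visit 7 (section 3.4.5) | stop drug, or leave study | stop on-demand drug if dispensed, or leave study |
| Visit 7 to year 10 (section 3.4.5; Tables 1 and 2, footnotes) | stop drug, or leave study | normally leave study only |

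Section 3.4.5 allows two further courses in operated subjects. One is 2–12 weeks for ulceration or erosion in the fundoplication arising within 3 months of surgery. The other is 2 weeks for an ulcer due to intermittent NSAID use.

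**2. Share of follow-up with unequal routes**

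Inputs: visit 7 at month 6 (Table 1); end of follow-up at year 10, that is month 120 (Table 2).

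- Share = (120 − 6)/120 = 114/120 = 95%.
- Latest case for a subject on the erosion course, assuming treatment starts when the lesion arises: surgery at month 3, lesion 3 months later at month 6, 12 weeks of treatment (about 2.8 months), ending near month 8.8. Share = (120 − 8.8)/120 = 111.2/120, or about 93%.

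The exceptions therefore change little. This is a share of calendar time, not an estimate of bias.

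**3. Both arms enter the safety population**

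Section 6.2.1 requires at least one dose of study drug and post-dose information. All subjects take esomeprazole in the run-in, so subjects randomized to surgery qualify, and their events fall under the same criterion.

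**4. Causality**

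- SAEs: asked for every event (section 4.4.2.1).
- Non-serious AEs leading to discontinuation: not among the items listed in section 4.4.2.2.

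For the second group, on the text available, only an all-cause count exists.

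**5. Can the count be separated?**

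Yes. Section 4.4.2.2 records action on the drug and discontinuation of the study as two items, and Table 4 itself includes "action taken to study drug due to AE" in the endpoint. SAEs are recorded whether or not anything is stopped, and reported whatever their cause (section 4.4.2.3), so their capture does not depend on having a drug to stop.

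**The case against.** The best defence has four parts.

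- **No comparison is planned.** Table 4 rules out a formal one, and neither it nor section 6.2.3 says the frequency will be shown by arm. This stands as a limit: presentation by arm is inferred from the comparative aim, and the point concerns descriptive reading only. It does not remove the asymmetry once the arms are shown together.
- **Restricted collection is disclosed and reasoned in section 4.4.** True. That explains why few non-serious AEs are collected, but not why the two triggers are merged.
- **Table layout belongs in the SAP.** Largely fair for the layout. The recording threshold and the list of recorded items, however, are fixed in the protocol, and a later plan cannot recover events or causality answers that were never collected.
- **Table 4 says only that the result will contribute to the reaction pattern.** This also stands, and it makes the causality gap secondary.

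Splitting the table does not remove the asymmetry either. Section 3.3.5.1 treats discontinuation from treatment and from assessments together, so in the medical arm a drug stop may often also be a study stop. The second line of the proposed table therefore needs a caution label.

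Stronger readings are tempting but unsupported. A reader might infer that causality is never asked; it is asked for every SAE. A reader might infer that operated subjects never have study drug; they may have it before surgery, on demand until visit 7, and in the short courses above. A reader might also infer a zero count after surgery and test it against an assumed medical-arm rate. The protocol gives no such rate, plans no test, and lets any subject leave for an unacceptable adverse event (section 3.3.5.1).

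**Conclusion.** The point holds as a limit on interpretation. For about 95% of the randomized period the drug-stop route is normally closed to operated subjects, so a between-arm reading of this frequency is not a like-for-like measure of tolerability. The rule tends to raise the medical-arm count relative to the surgical one. By how much cannot be computed from the protocol. For non-serious AEs the frequency is all-cause and is not by itself an adverse-drug-reaction frequency.

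This rests on two assumptions: that the safety tables will be read by arm, as the stated aim implies, and that the items listed in section 4.4.2.2 are complete, since the case report form and Appendix F are not available here. The change should be made, because it alters what may be concluded about tolerability. It does not touch the primary analysis.

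**What to change.** In Table 4 and section 6.2.3, use the items already recorded under section 4.4.2.2 to report separately:

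1. SAEs, both arms.
2. AEs leading to discontinuation from the study, both arms, labelled as not directly comparable.
3. AEs leading to stopping esomeprazole, medical arm only, as drug tolerability without a surgical comparator.

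Base any between-arm tolerability statement on SAEs.

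For causality, choose one of two options. Either add the existing yes/no question prospectively for AEs leading to discontinuation, or state that the non-serious count is all-cause and is not an adverse-drug-reaction frequency.

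The cost of the split is a slightly longer table, with no new data and no change to any clinical rule. The causality item would cover later events only: the first subject entered in Q4 2001 and the prolongation starts in Q1 2007 (section 7.8), so an item added then misses roughly the first five years. The statement option costs one sentence.

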#### **4.4.2 Adverse Events**

##### **4.4.2.1 Definitions**

The definitions of adverse events (AEs), serious adverse events (SAEs) and other significant adverse events (OAEs) are given below. It is of the utmost importance that all staff involved in the study is familiar with the content of this Section. The principal investigator is responsible for ensuring this.

## **Adverse Event**

An adverse event is the development of an undesirable medical condition or the deterioration of a pre-existing medical condition following or during exposure to a pharmaceutical product, whether or not considered causally related to the product. An undesirable medical condition can be symptoms (e.g., nausea, chest pain), signs (e.g., tachycardia, enlarged liver) or the abnormal results of an investigation (e.g., laboratory findings, electrocardiogram). In clinical studies, an AE can include an undesirable medical condition occurring at any time, including run-in or washout periods, even if no study treatment has been administered.

## **Serious Adverse Event**

A serious adverse event is an AE occurring during any study phase (i.e., run-in, treatment, washout, follow-up), and at any dose of the investigational product, comparator or placebo, that fulfils one or more of the following criteria:

- results in death
- is immediately life-threatening
- requires in-subject hospitalization or prolongation of existing hospitalization
- results in persistent or significant disability or incapacity
- is a congenital abnormality or birth defect
- is an important medical event that may jeopardize the subject or may require medical intervention to prevent one of the outcomes listed above

The causality of SAEs (i.e., their relationship to study treatment) will be assessed by the investigator(s), who in completing the relevant case report form must answer “yes” or “no” to the question “Do you consider that there is a reasonable possibility that the event may have been caused by the drug?” For further guidance on the definition of a SAE and a guide to the interpretation of the causality question, see Appendix F.

## **Other significant adverse event**

An AstraZeneca expert will identify OAEs during the evaluation of safety data for the Clinical Study Report. Significant adverse events of particular clinical importance, other than SAEs and those AEs leading to discontinuation of the subject from study treatment, will be classified as OAEs. Examples of these are marked haematological and other laboratory abnormalities, and certain events that lead to intervention (other than those already classified as serious), dose reduction or significant additional treatment. For each OAE, a narrative will be written and included in the Clinical Study Report.

#### 4.4.2.2 Recording of adverse events

SAEs and AEs causing premature discontinuation of study drug and/or study will be recorded retrospectively by the investigator in the Case Report Form at visit 2 and the following visits. If any SAE or AE causing premature discontinuation of study drug and/or study are ongoing at the subjects last visit in the study, they must be followed up after 2 to 4 weeks and thereafter as long as medically indicated. This can be done either as an extra visit to the clinic or by written or verbal contact with the subject.

Spontaneously reported SAEs and AEs causing premature discontinuation of study drug and/or study, objective findings and observations, and SAE and AEs causing premature discontinuation of study drug and/or study reported in response to the standardized question “Have you had any health problems since the previous visit?” will be recorded in the CRF. Start and stop date (or marked as ongoing), outcome, maximum intensity, seriousness, and action taken with regard to investigational product and if the AE caused subject to discontinue the study will be recorded. Maximum intensity will be rated according to the following scale:

- |              |  |
|--------------|--|
| 1 = Mild     | - awareness of sign or symptom, but easily tolerated                 |
| 2 = Moderate | - discomfort sufficient to cause interference with normal activities |
| 3 = Severe   | - incapacitating, with inability to perform normal activities        |

It is important to distinguish between serious and severe AEs. Severity is a measure of intensity whereas seriousness is defined by the criteria in Section 4.4.2.1. An AE of severe intensity need not necessarily be considered serious. For example, nausea, which persists for several hours, may be considered severe nausea, but not a SAE. On the other hand, a stroke which results in only a limited degree of disability may be considered a mild stroke but would be a SAE.

Abnormal test results from laboratory investigations or endoscopy investigations (including biopsies) that meet any criteria of an SAE must be reported in accordance with the SAE reporting procedures (see Section 4.4.2.3).

Symptoms included in the efficacy variables

- Section 4.3.5.1 GERD symptoms (i.e. heartburn, acid regurgitation, dysphagia)
- Section 4.3.5.1. other GI symptoms (i.e. epigastric pain, flatulence, bloating, ability to vomit, ability to belch, diarrhoea)
- Section 4.3.7. Post-operative symptoms (i.e. post-operative hospital stay, abdominal infection, other abdominal complications, pulmonary complications, cardiac complications, other complications, in hospital post-operative death, other post-operative symptoms)

will only be recorded as AEs if they result in discontinuation of the study drug and/or study. If a sign or symptom meets any of the criteria of an SAE according to the definition (see Section 4.4.2.1) it must be reported as SAE.

Should a pregnancy occur, it must be reported in accordance with the procedures described in Section 9.4. Pregnancy in itself is not regarded as an AE unless there is a suspicion that an investigational product may have interfered with the effectiveness of a contraceptive medication.

Adverse events will be classified by AstraZeneca staff according to the terminology of the Medical Dictionary for Regulatory Activities (MedRA).

